## **6.9. Subject Replacement**

Only subjects missing doses or discontinuing at random (non-informative) before the primary visit on Day 14 will be replaced as originally randomized to receive rhu-pGSN or placebo. Safety data from all subjects treated with e 1 dose will be collected. Subjects discontinuing the study after the Day 14 visit will not be replaced.

## **6.10. Criteria for Study Termination**

The Sponsor reserves the right to discontinue the study at any time for any reason. Such reasons may be any of, but not limited to, the following:

- Occurrence of AEs unknown to date in respect to their nature, severity, and duration, or the unexpected incidence of known AEs
- Medical or ethical reasons affecting the continued performance of the study

If the study is prematurely terminated, the Investigator is to promptly inform the study subjects and Independent Ethics Committee (IEC) and should ensure appropriate follow up for the subjects. All procedures and requirements pertaining to the archiving of study documents should be followed. All other study materials (e.g., study drug, etc.) must be destroyed or returned to the Sponsor.

## 7. STUDY POPULATION

### 7.1. Number of Subjects

Part 1: A total of 60 evaluable participants randomized 1:1 to rhu-pGSN:placebo (30:30 subjects).

Part 2: A total of 20 evaluable participants randomized 1:1 to rhu-pGSN:placebo (10:10 subjects).

### 7.2. Subject Inclusion Criteria

To be considered eligible to participate in this study, a subject must meet all the inclusion criteria listed below:

1. Hospitalized with laboratory-confirmed (RT-PCR+) or highly suspected (compatible with at least bilobar lung involvement without another plausible diagnosis) COVID-19
2. Age ≥ 18 years
3. **Part 1 only:** Weight ≥ 100 kg
4. **Part 1 only:** Within 24 hours of reaching a WHO severity score of 4-6 either:
  - a) At admission
  - b) While already hospitalized.
5. **Part 2 only:** Within 24 hours of intubation without ECMO with a WHO severity score of 6 or 7)
6. Informed consent obtained from subject/next of kin/legal proxy
7. Primary admitting diagnosis of pneumonia supported by a compatible clinical presentation with a documented infiltrate consistent with pneumonia on CXR or CT, as assessed by the admitting emergency department (ED), clinic, or ward physician or equivalent caregiver
  - Recommended (not mandatory) guidance/discretionary criteria defining patients with pneumonia satisfying all 4 categories below:
    - At least 2 symptoms: difficulty breathing, cough, production of purulent sputum, or chest pain
    - At least 2 vital sign abnormalities: fever, tachycardia, or tachypnea (thresholds -- fever: body temperature >100.4°F [38°C]; heart rate >100 beats/min; respiratory rate >24/min)
    - At least one finding of other clinical signs and laboratory abnormalities: hypoxemia (O2 saturation <90%), clinical evidence of pulmonary consolidation, or leukocytosis ≥ 1.5x10^4 or leukopenia <4x10^3
    - Chest imaging or CT chest showing at least bilobar pulmonary infiltrates
      - Principal Investigator (PI) to note radiologic findings in the eCRF
      - Radiology report and conclusion should be summarized in the eCRF

- A copy of the radiograph attached to be saved for review, if possible
- 8. A hyperinflammatory status (defined by increased ferritin ≥ 500 µg/L, D-dimer ≥ 1000 ng/mL, or CRP ≥ 75 mg/L)
- 9. During the course of the study starting at screening and for at least 6 months after their final study treatment:
  - a) Female subjects of childbearing potential must agree to use 2 medically accepted birth control methods
  - b) Male subjects with a partner who might become pregnant must agree to use reliable forms of contraception (i.e., vasectomy, abstinence), or an acceptable method of birth control must be used by the partner
  - c) All subjects must agree not to donate sperm or eggs (ovocytes)

### **7.3. Subject Exclusion Criteria**

To be eligible for entry into the study, the subject must not meet any of the exclusion criteria listed below:

1. A negative RT-PCR test for COVID-19 in the absence of a positive test during the evaluation of the present illness (in the presence of a positive test during the current illness, preceding or subsequent negative tests do not disqualify the subject)
2. Extracorporeal membrane oxygenation (ECMO)
3. Pregnant or lactating women
4. Active underlying cancer treated with systemic chemotherapy or radiation therapy during the last 30 days
5. Transplantation of hematopoietic or solid organs
6. Chronic mechanical ventilation or dialysis
7. Otherwise unsuitable for study participation because of chronic, severe, end-stage, and life-limiting underlying disease unrelated to COVID-19 likely to interfere with management and assessment of acute pneumonia, only comfort or limited (non-aggressive) care is to be given, or life expectancy <6 months unrelated to acute COVID infection in the opinion of the Investigator

Notes:

- PK sampling is strongly encouraged. However, participants refusing some or all PK blood sampling can remain in the trial.
- Participants with superinfection in addition to COVID-19 are eligible.
- Caregivers can decide whether any other medications (investigational or otherwise) should be administered.

### **7.4. Subjects or Partners of Subjects of Reproductive Potential**

Pregnancy is an exclusion criterion. Women of childbearing potential (<60 years of age and/or not post-hysterectomy) must avoid getting pregnant during the study. Female subjects of childbearing potential must have a negative serum or urine pregnancy test within 24 hours prior to start of study drug. A serum or urine pregnancy test will be performed at the EOS Visit.

Women of childbearing potential should not become pregnant while on this study, or for 6 months after receiving the last dose of study treatment. Females that can become pregnant must agree to use two medically accepted birth control methods during the study starting at screening and for at least 6 months after their final study treatment. Medically accepted forms of birth control include condoms, diaphragm, cervical cap, the placement of an intrauterine device (IUD), birth control pills, hormone implants or injections, or partners who have undergone a vasectomy (surgical sterility). Unless sterilized, one of these methods must be a barrier method such as a condom or diaphragm. Abstinence at certain times of a menstrual cycle and partner withdrawal are not acceptable methods of birth control. The subject should consult with her study doctor about the contraceptive methods that are available, and which might be the best for her.

Male subjects with a partner who might become pregnant must use reliable forms of contraception (i.e., vasectomy, abstinence) during the study starting at screening and for at least 6 months after their final study treatment, or an acceptable method of birth control must be used by the partner (i.e., oral contraceptive, IUD, hormonal implants, contraceptive injection, or a double- barrier method).

Subjects will be instructed to notify the Investigator if pregnancy is discovered either during or within 6 months of the last dose of study drug.

Subjects must agree not to donate sperm or eggs (ovocytes) during the study starting at screening and for at least 6 months after their final study treatment.

## **7.5. Waivers of Inclusion/Exclusion Criteria**

No waivers of these inclusion or exclusion criteria ([Section 7.2](#) and [Section 7.3](#)) will be granted by the Investigator and/or the Sponsor or its designee for any subject enrolling into the study.

## 8. DESCRIPTION OF STUDY TREATMENT

### 8.1. Description of Study Drug

Study drug is a recombinant human plasma gelsolin (rhu-pGSN) powder for solution ([Table 4](#)).

Study drug will be administered to subjects randomized to rhu-pGSN as an IV bolus at a rate between 5 and 20 mL/min through a standard 0.2-micron filter at 12 mg/kg (based on actual body weight) at 0, 12, and 36 hours ( $\pm$  60 minutes).

rhu-pGSN drug product is provided as lyophilized powder containing 200 mg rhu-pGSN plus excipients. It is provided in 10-mL glass vials to be reconstituted to a volume of 5 mL with 4.56 mL of sterile water yielding a final concentration of 40 mg/mL of rhu-pGSN, 2% glycine, 4% trehalose, 0.5% arginine, and 0.1% poloxamer 188 in a 10-mM phosphate buffer, pH 7.

**Table 4: Investigational Product**

	Investigational Product
Product Name:	rhu-pGSN
Dosage Form:	Powder for solution filled as a 5 mL fill in 10-mL glass vials
Unit Dose	rhu-pGSN reconstituted to a volume of 5 mL with 4.56 mL of sterile water
Route of Administration	Intravenous
Physical Description	Lyophilized powder
Storage Conditions	2 to 8 °C
Manufacturer	Drug Product: Integrity Bio, Inc., Camarillo, CA USA

Vials containing rhu-pGSN study drug will be labeled according to national regulations for investigational products.

### 8.2. Description of Placebo

Placebo will be normal saline solution and will be dosed at a volume of 0.30 mL/kg of 0.9% saline solution via IV push [matching the volume of rhu-pGSN for a subject of that size] injected at 5 to 20 mL/min through a standard 0.2-micron filter at 0, 12, and 36 hours ( $\pm$  60 minutes). The placebo requires no special manipulation.

### **8.3. Preparation of Study Drug for Administration**

The Investigator or designee will be responsible for administering the appropriate dose of IV rhu-pGSN to subjects. rhu-pGSN must be stored refrigerated at 2 to 8 °C in its original package in an appropriate storage facility accessible only to the pharmacist(s), the Investigator, or a duly designated person.

This person will determine the dose (mg) of rhu-pGSN, calculate the volume of rhu-pGSN solution needed, and reconstitute each vial of study drug to a volume of 5 mL with 4.56 mL of sterile water.

The individual rhu-pGSN IV push will be prepared under aseptic conditions and administered at the study site according to the directions of the Sponsor, which will be provided in a Pharmacy Manual. Any powder remaining in the vial must be discarded. After dilution, administration of rhu-pGSN should be initiated ASAP (within 4 hours, including no more than 2 hours at room temperature). Maximum allowed storage times and conditions will be detailed in the Pharmacy Manual.

### **8.4. Subject Monitoring During rhu-pGSN Administration**

Vital signs should be measured as outlined in [Section 9.2.2](#). All supportive measures consistent with optimal patient care will be provided throughout the study according to institution standards.

Precautions for anaphylaxis should be observed during rhu-pGSN administration. Emergency resuscitation equipment and medications should be readily available. Additional supportive measures should also be available and may include, but are not limited to, epinephrine, antihistamines, corticosteroids, IV fluids, vasopressors, oxygen, bronchodilators, diphenhydramine, and acetaminophen (paracetamol).

### **8.5. Study Drug Administration**

The subject will receive an IV bolus at the time points specified in [Table 5](#) at a rate between 5 to 20 mL/min. The syringe, filter, and extension tubing should be connected after disconnecting the IV as close to the subject as possible.

Subjects are to be monitored for administration site reactions during study drug administration and for 1 hour after its completion. Injection-site reactions will be recorded as AEs using the appropriate coding terms on the eCRF.

### **8.6. Shipment of Study Drug**

Prior to study treatment, study medications will be supplied to the clinical trial site's pharmacy or equivalent by the Sponsor or its designee.

Shipment of study drug supplies for the study will be accompanied by a shipment form describing the contents of the shipment, drug information, and other appropriate documentation. The shipment form will assist in maintaining current and accurate inventory records.

## **8.7. Receipt and Storage of Study Drug**

All study supplies should arrive at the pharmacy or equivalent in sufficient quantity and in time to enable dosing as scheduled. The pharmacist or designee must ensure the acknowledgement of receipt of the clinical trial material (i.e., study drug) at the site, including that the material was received in good condition.

The Sponsor or its designee must notify the pharmacist or designee prior to dispatch of drug supplies, with the anticipated date of their arrival, addressed to the site's pharmacy.

The investigational drug will be stored in the pharmacy or equivalent, refrigerated at 2 to 8 °C. The Sponsor should be notified for any deviation from the storage conditions.

## **8.8. Accountability, Handling, and Disposal of Study Drug**

The study site must maintain accurate records documenting dates and amount of study drug received. The trial site's pharmacy or equivalent will be responsible for ensuring the supervision of the storage and allocation of these supplies. When a shipment is received, the pharmacist or designee verifies the quantities received and the accompanying documentation and provides acknowledgement of receipt.

Accountability logs will be provided to assist the pharmacist or designee in maintaining current and accurate inventory records covering receipt, dispensing, and disposition of the study drug. An unblinded study monitor will examine inventory during the study. Accountability records must be readily available and may be subject to inspection by regulatory authorities or independent auditors at any time.

Drug administration will be recorded in source documents and in the eCRFs.

At the end of the study, delivery records of study drug will be reconciled with used / unused supplies. A disposition form will be completed as per local regulation, since used/partially used vials might be required to be destroyed after use. Unused vials should be returned to the Sponsor. One copy of all accountability records and the disposition form will be retained by the Investigator for the study files.

## **8.9. Concomitant Medications**

To date, there are no known drug interactions with rhu-pGSN. Because rhu-pGSN has no effect on the cytochrome p450 (CYP450) system, subjects may continue their present medications as directed by their caregivers. Subjects may receive concomitant medications to treat symptoms, AEs, and inter-current illnesses that are medically necessary as standard care.

Medications administered within 1 month prior to screening and concomitant medications, including generic name (if possible), and start date if known should be documented in the subject's file and in the eCRF.

## **8.10. Method of Assigning Subjects to Treatment Groups**

Subjects will be randomized in a 1:1 ratio to receive SOC plus IV rhu-pGSN or placebo during the treatment period. See [Section 8.12](#) for details regarding randomization.

## **8.11. Treatment Compliance**

The study drug will be administered by personnel at the study site to ensure compliance.

## **8.12. Randomization and Blinding**

Following screening, subjects qualified for study entry will be randomized to receive rhu-pGSN or placebo during the treatment period. Randomization will be done centrally using manual methods. All eligible subjects will be assigned a randomization number.

The investigational site team and the subject will be kept blinded to the treatment allocation of each participant. Only the designated pharmacist(s) or designee(s) will be unblinded to the treatment allocation. A manual system to randomly assign a treatment allocation. The treatment allocation will be available to the unblinded pharmacist(s).

### **8.12.1. Unblinding**

The unblinded pharmacist(s) or designees will prepare sterile syringes with filters consisting of 12 mg/kg rhu-pGSN or normal saline ([Section 8.3](#)) according to the treatment allocation for each subject.

There is no antidote for rhu-pGSN. Unblinding should only be performed if knowledge of the treatment assignment will change the planned management of a medical condition. If possible, prior to unblinding, the need to unblind should be discussed with the Medical Monitor or Sponsor's Chief Medical Officer; however, this should not delay unblinding if the Investigator believes it is necessary. Each case of unblinding will be documented and documentation will be stored separately by the unblinded pharmacist or designee.

Subjects that are unblinded may be withdrawn from the study. The decision to withdraw a subject from the study because of unblinding should be discussed with the Sponsor. If the subject is withdrawn, the Investigator or designee must record the date and reason for withdrawal on the appropriate eCRF for that subject.

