## **6.8. Criteria for Treatment Discontinuation**

Subjects are free to discontinue their participation in the study at any time and without prejudice to further treatment. The Investigator must withdraw any subject from the study if that subject requests to be withdrawn, or if it is determined that continuing in the study would result in a significant safety risk to the subject.

The subject's participation in this study may be discontinued for the following reasons:

- Subject withdrew consent
- Unacceptable AE
- Subject is unwilling or unable to continue the study or is lost to follow up
- Subject is non-compliant with study procedures/study protocol
- Investigator decides that withdrawal from the study is in the best interest of the subject
- Any clinically significant change in subject's medical condition (at the discretion of the Investigator)
- Sponsor decision to end the study

If a subject withdraws from the study prematurely, assessments scheduled for the EOS Visit should be performed ASAP. If a subject refuses further assessment, the subject should be contacted for safety evaluations (AE/concomitant medications/potential pregnancy) approximately 28 and 90 days after study withdrawal.

If such withdrawal occurs, or if the subject refuses to participate in the EOS Visit, the Investigator must determine the primary reason for a subject's withdrawal from the study and record the information on the electronic case report form (eCRF). If the reason for withdrawal is an AE, monitoring should continue until the outcome is evident. The specific event or test result(s) must be recorded in the eCRF. At the discretion of the Sponsor, subjects may also be removed from the study.

It should be clearly documented in the source data whether a subject withdrew his/her consent and will not enter the follow-up phase, or if a subject withdrew his/her consent for study drug treatment but will continue further participation in the study.

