## 11. STATISTICS

### 11.1. General Overview

All subjects given e 1 dose of study drug will be included in the Full Analysis Set (FAS) according to actual drug received; non-completers will be counted as failures in the primary efficacy analysis. Subjects receiving all 3 doses and evaluable for the primary Day 14 endpoint will constitute the per-protocol population for efficacy assessment. WHO severity score will be recorded daily while the subject is hospitalized, after discharge through Day 14, where feasible, and at each follow-up visit.

AE data will be summarized for the FAS by actual drug received using counts and proportions of subjects having an AE, each AE type, and an AE of each System Organ Class. SAEs and reasons for any early discontinuation will be summarized similarly. All deaths will be categorized by cause of death as per investigator assessment and relationship to study drug and/or COVID-19

Immunogenicity will be assessed on Days 1(predose), 28, and 90 days in all participants. Antibodies against pGSN will be assayed from frozen specimens to determine whether the investigational product induces an antibody response in recipients.

For Part 1, binary efficacy endpoints will be compared between treatments via stratified Cochran-Mantel-Haenszel (CMH) test and, to accommodate continuous covariates, via logistic regression. Continuous efficacy and biochemical endpoints will be compared between treatments via mixed model repeated measures analysis or analysis of covariance, depending on whether repeated measures are available or not. Time-to-event analysis via stratified log rank test and Cox proportional hazards model may also be carried out as supplemental analyses.

For Part 1, exploratory analyses looking at biomarkers and outcomes in each treatment arm will be conducted. Other exploratory analysis to compare the efficacy endpoint data from the rhu-pGSN group from this study to that of external control data may be carried out if appropriate. Sample size may be increased to improve the precision of the estimates of between-treatment comparisons if appropriate and if drug supplies are available.

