11.5 Discontinued Subjects

Discontinued subjects will have safety assessments taken at Early Withdrawal visits. These will be presented separately and will not be combined with EOS if results are available.

The reason for discontinuation from the study will be mapped in the analysis as follows:

Primary reason for early discontinuation (As in CRF)	Reason for early termination from the study
Subject withdrew consent	Subject withdrew consent
Unacceptable AE	Unacceptable AE
Pregnancy	Pregnancy
Subject is unwilling or unable to continue the study or is lost to follow up	Subject unwilling / lost to follow-up
Subject is non-compliant with study procedures/study protocol	Protocol Deviation
Investigator decides that withdrawal from the study is in the best interest of the subject	At the discretion of the Investigator
Any clinically significant change in subject's medical condition (at the discretion of the Investigator)	At the discretion of the Investigator due to change in medical condition
Treatment unblinded	Treatment Unblinded
Sponsor decision to end the study	Sponsor decision to end the study
Death	Death
Other	Other

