12.9.1 Primary Efficacy analysis

12.9.1.1 Proportion of Subjects Alive on Day 14

Number and percentage of subjects alive on Day 14 without the following will be summarized. Percentages will be based on the corresponding analysis set. Subjects who discontinued from the study early or whose survival status is inconclusive on Day 14 will be considered as failure (Not Alive).

- Ongoing use of vasopressors
- Ongoing intubation/mechanical ventilation
- New ongoing need for dialysis/renal replacement therapy (RRT)

The proportion of subjects alive will be compared across treatment arms using a Cochran-Mantel-Haenszel (CMH) method. The common Risk Difference along with associated 80% CI will be reported. Unadjusted p-value for testing the null hypothesis that there is no strong correlation between treatment and subject status will also be reported. As this is a pilot Phase 2 proof-of-concept (POC) trial in an infection with no approved therapy and false negative error (100% minus power) is equally as important as false positive error, the one-sided type 1 error is set at 0.2.

Reference SAS Program:

```
proc freq data= ;
  tables <status>*<treatment> / cmh riskdiff(common) alpha=0.2;
run;
```

The analyses will be based on FAS and repeated for Per-Protocol Analysis Set.

In DDP: Tables 14.2.1.1 and 14.2.1.2, Listing 16.2.6.2, 16.2.6.3, and 16.2.6.4

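### An unblinded subject may be withdrawn at discretion and then scored as a Day 14 failure, so a decision taken when the arm may be known could set that subject's primary outcome

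*Protocol*

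**What the plan says.** **Unblinding and withdrawal.** Protocol 8.12.1 limits code breaks to medical need: "Unblinding should only be performed if knowledge of the treatment assignment will change the planned management of a medical condition". It continues: "Subjects that are unblinded may be withdrawn from the study". The only procedure attached is that "The decision to withdraw a subject from the study because of unblinding should be discussed with the Sponsor", plus recording the date and reason if the subject leaves. SAP 4.4 repeats the rule. SAP 11.5 gives it its own discontinuation category, "Treatment unblinded". Protocol 6.8 adds a general power not tied to unblinding: "At the discretion of the Sponsor, subjects may also be removed from the study".

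**Scoring.** Protocol 11.1 states that "non-completers will be counted as failures in the primary efficacy analysis". SAP 12.9.1.1 states that "Subjects who discontinued from the study early or whose survival status is inconclusive on Day 14 will be considered as failure", with no exception by reason. The primary set is the FAS: everyone given at least one dose (SAP 10.4). SAP 11.17, which defines the primary criterion flag, reads differently. It flags every FAS subject whatever the disposition, and turns only an unclear status into a failure.

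**After withdrawal.** Protocol 6.8 asks for the end-of-study assessments promptly. For a subject who refuses further assessment, it asks for safety contact about 28 and 90 days after withdrawal. Protocol 10.1.2 requires SAEs to be recorded to 90 days after the last dose. SAP 11.18 censors a subject without a death in the trial at withdrawal or last visit, whichever is earlier.

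**The concern.** A code break for medical need is legitimate. The difficulty is the step from code break to study withdrawal. That step is optional, has no criterion, and is taken by an investigator who may by then know the arm, in discussion with the sponsor. The scoring rule turns it into a primary endpoint failure regardless of how the subject was doing on Day 14.

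The three doses are complete 36 hours after the first (Protocol 6.5), whereas the endpoint is read on Day 14. Protocol 6.8 already distinguishes a subject who stops study drug but stays in the study from one who does not enter follow-up. Nothing in the analysis needs an unblinded subject to leave follow-up.

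What is at stake is the independence of the primary outcome from treatment knowledge, in a trial small enough for one subject to matter.

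**Working it through.** **1. The chain through the documents.** Code break (Protocol 8.12.1) → optional withdrawal (Protocol 8.12.1, SAP 4.4) → recorded discontinuation (SAP 11.5) → failure in the FAS (Protocol 11.1, SAP 12.9.1.1). Three provisions might undo the last step:

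- *Per-protocol analysis.* SAP 10.6 requires completion of Day 14, so it drops the subject and does not recover the outcome.
- *Replacement.* Protocol 6.9 limits this to non-informative dropout. SAP 11.6 counts the replacement like any other subject, and the dosed original stays in the FAS.
- *Criterion flag.* SAP 11.17 could make a withdrawn subject known to be alive and off support a success, which conflicts with SAP 12.9.1.1. It does not rescue a subject withdrawn while ventilated, because SAP 11.16.1 then treats ventilation as ongoing at Day 14.

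**2. The plan's own figures.** Inputs from Protocol 11.2: 20% vs 5%, one-sided alpha 0.2, N = 54 (27 per arm). I read 20% and 5% as failure proportions, the only reading under which 5% on rhu-pGSN is a benefit.

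Power = Φ[(Δ − 0.8416·SE₀)/SE₁], with SE₀ = √(2p̄(1−p̄)/n) and SE₁ = √{[p₁(1−p₁)+p₂(1−p₂)]/n}.

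- SE₀ = √(2×0.125×0.875/27) = 0.0900 and SE₁ = √((0.16+0.0475)/27) = 0.0877.
- Power = Φ[(0.15 − 0.0758)/0.0877] = 80.1%. The stated ~80% reproduces.
- 20% vs 11.6%: z = 0.084/√(2×0.158×0.842/27) = 0.846, one-sided p = 0.199. The stated 8.4 points reproduces.

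**3. Weight of one reclassified subject.** 1/27 = 3.7 points, or 3.7/8.4 = 44% of the threshold at the design it was computed for. At the planned 30 per arm (Protocol 7.1), 1/30 = 3.3 points.

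**4. Can one subject reverse the result?** Pooled z-test, 30 per arm, failures on placebo vs rhu-pGSN:

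- 6 vs 3: z = 0.100/√(0.15×0.85×2/30) = 1.085, p = 0.139, significant at 0.2.
- 6 vs 4 (one rhu-pGSN success rescored): z = 0.0667/√(0.1667×0.8333×2/30) = 0.693, p = 0.244, not significant.
- 7 vs 4 (then one placebo success rescored): z = 0.100/√(0.1833×0.8167×2/30) = 1.001, p = 0.158, significant again.

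**5. Illustration for k cases.** The documents give no count, so k = 1 to 3, all in one arm, is an assumption. Each case adds 1/n to that arm's failure rate in the formula above. Example, k = 1 on rhu-pGSN at 27 per arm: p₂ = 0.05 + 0.037 = 0.087, Δ = 0.113, and power = Φ[(0.1130 − 0.0803)/0.0942] = 63.6%. In the last column the true failure rate is 20% in both arms.

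| k | Power, cases on rhu-pGSN (27 / 30 per arm) | Power, cases on placebo (27 / 30) | Rejection rate with no true effect, cases on placebo (27 / 30) |
|---|---|---|---|
| 0 | 80.1% / 82.6% | 80.1% / 82.6% | 20.0% / 20.0% |
| 1 | 63.6% / 67.7% | 87.7% / 89.2% | 30.4% / 29.9% |
| 2 | 46.6% / 51.7% | 92.8% / 93.6% | 42.0% / 40.8% |
| 3 | 31.9% / 37.0% | 96.1% / 96.5% | 53.8% / 52.1% |

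**The case against.** The case on the other side is substantial.

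- **Few cases, and sick ones.** Unblinding is restricted to medical need. Such subjects may be deteriorating and may fail on Day 14 anyway, in which case the rule changes nothing. Withdrawal is permitted, not required. This stands, and it is why the conclusion is *could change*.
- **The arithmetic is not about unblinding.** Any one subject weighs 1/n. The table shows sensitivity and is no estimate of bias. This stands.
- **Scoring is not settled.** SAP 11.17 can be read to keep an observed success. This stands as an unresolved conflict, not as a safeguard, because SAP 12.9.1.1 states the opposite for the primary analysis.
- **Cases would be visible.** SAP 11.5 and 12.1 tabulate the reason by arm. That discloses the problem without recovering the Day 14 outcome.

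A reader might also infer that withdrawal cuts off 90-day safety follow-up and so biases the SAE endpoint. The documents do not support that. Protocol 10.1.2 still requires SAE recording to 90 days, Protocol 10.7 has events followed until resolution, withdrawal of consent, loss, death or end of study, and Protocol 6.8 provides for end-of-study assessments and, after refusal, safety contacts. The gap is narrower: nothing secures Day 14 support status after withdrawal. For a subject withdrawn by others' decision, Protocol 6.8 sets no contact after the prompt end-of-study assessment. Censoring under SAP 11.18 also shortens the survival analysis.

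**Conclusion.** The point holds in limited form. The plan leaves a route by which a discretionary decision, taken when the arm may be known, could determine a subject's primary outcome. It operates only for a dosed subject withdrawn before Day 14 who would otherwise have been a success, and only if SAP 12.9.1.1 prevails over SAP 11.17.

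Each such subject is worth 3.7 points at 27 per arm or 3.3 at 30 per arm, and one can move the result across the significance line in either direction. The number of cases is unknown and likely small. It would be too strong to say that the rule does change the primary endpoint, or that either primary endpoint is biased. The power and rejection rates rest on an assumed count, all cases falling in one arm, and 20% and 5% being failure proportions. The point merits correction because the repair is cheap.

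**What to change.** - **Protocol 8.12.1 and SAP 4.4:** state that unblinding alone is not a reason for withdrawal from study follow-up. Unblinded subjects stay in the scheduled visits to Day 90 unless they withdraw consent. Limit the SAP 11.5 category to match. This concerns data collection only and leaves decisions on remaining doses untouched.
- **SAP 12.9.1.1 and 11.17:** reconcile them so that an unblinded subject's observed Day 14 status is used, with failure only if that status is unknown. Bring the non-completer sentence in Protocol 11.1 and the carry-forward rule in SAP 11.16.1 into line.
- **SAP 11.18:** with follow-up kept, censor at the last date known alive and not at the code break.
- **Sensitivity analysis:** flag unblinded subjects, report their number by arm, and repeat the primary comparison with all of them scored as failures.

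The cost is small wording amendments and one added sensitivity analysis. The visits are already scheduled. With observed status used, the design figures stand: 80.1% power at 27 per arm and 82.6% at 30 per arm.
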